inhalation of an ultrafine aerosol of carbon nanoparticles labeled with ^{99m}Tc (UFCNPA, ^{99m}Tc) obtained from the TechnegasPlus generator.

3. A brief description of the known and potential risks to study patients, if any.

UFCNPA, ^{99m}Tc remains a safe drug for ventilation research because it does not have any potentially fatal or adverse results, reactions, consequences or complications that are associated with it, and has been used in clinical practice for more than three decades and can be used safely and successfully in patients.

Adverse effects associated with the use of UFCNPA, ^{99m}Tc , were mainly reported prior to the early 1990s. Notably, among these effects was transient hypoxia caused by an average 8.5% decrease in oxygen saturation during inhalation of UFCNPA, ^{99m}Tc . Given the fact that, prior to publication of this study, a significant number of ventilation studies had already been carried out without any adverse effects, the authors concluded that a temporary decrease in oxygen saturation does not appear to pose a risk to patients.

Currently, more than 2,500 Technegas generators are in use in 51 countries, where nearly 200,000 diagnostic examinations are performed annually. Since 1986, more than 2 million injections of UFCNPA, ^{99m}Tc have been performed for ventilation lung scintigraphy, including in young children, the disabled, the elderly and patients on mechanical ventilation, without any reports of adverse effects and side effects [3, 4, 5].

The global incidence of adverse reactions to radiopharmaceuticals used in diagnostics is generally very low, reported to be approximately 2-3 persons per 100,000 or even less (ie 1.3 per 100,000) [6].

Dangers when using the TechnegasPlus Medical Generator:

- Dangers that could arise from lack of maintenance. The identified situations can lead to unnecessary additional exposure of the operator and / or patient with a small dose of radiation. Radiation can be spread through the air due to worn or damaged O-rings, lack of protective filtration, for example, when a filter is not installed. The identified hazards were eliminated thanks to design solutions and, in addition, by the regulation of periodic maintenance of the device.

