To date, several pilot articles have been published in which the authors have demonstrated the feasibility and safety of low-dose irradiation in patients with COVID-19 associated with viral pneumonia [9, 10]. In the article "Low-Dose Whole-Lung Radiation for COVID-19 Pneumonia: Planned Day-7 Interim Analysis of a Registered Clinical Trial", the authors irradiated the entire lung volume with a dose of 1.5 Gy per 1 fraction in

five patients with various concomitant diseases, and the presence of severe respiratory distress requiring oxygen support. Within 24 hours after the session, 3 (60%) patients were removed from auxiliary methods of oxygenation, 4 people (80%) achieved CT-confirmed regression of pneumonia, no acute toxicity associated with radiation therapy was noted [9].

5. Goals and objectives of scientific research.

Objective: To determine the possibility, safety and effects of the use of inhaled low-dose radionuclide therapy in the complex treatment of patients with COVID-19 - associated viral pneumonia.

Tasks:

1. To investigate the dosimetric characteristics of the applied technique on anthropometric phantoms to obtain the coefficients of the transition from the rate of counting pulses over the region of interest to the activity contained in this region (in kBq).
2. To determine the accumulated dose in human lungs during internal irradiation of ^{99m}Tc in a group of healthy volunteers.
3. To develop a methodology for the use of inhaled low-dose radionuclide therapy in complex treatment of patients with COVID-19 - associated viral pneumonia.
4. To assess the possibility of using inhaled low-dose radionuclide therapy in the complex treatment of patients with COVID-19 - associated viral pneumonia.

6. Research design

At the first stage of preparation for the study, to obtain the coefficients of the transition from the pulse count rate over the region of interest to the absolute activity of ^{99m}Tc in the region of interest (in kBq), measurements will be made on a human phantom (see Section 7.3.1).

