At the second stage of preparation for the study to determine the accumulated absorbed dose in the lungs of a volunteer under internal irradiation of ^{99m}Tc after inhalation of UFCNPA, ^{99m}Tc obtained from the TechnegasPlus generator into the crucible of which an activity equal to 833MBq is loaded, a group of 5 volunteers without clinical and radiological signs of pneumonia will be preliminarily formed. For this purpose, at the initial stage, patients from this group will undergo: thermometry and physical examination, as well as X-ray CT of the thoracic organs. In addition, given the importance of immunological criteria in the pathogenesis of Covid-19, it is advisable to assess the immune status and the level of blood cytokines (pro-inflammatory cytokines: TNF α , IL-6, IL-12 TNF- α 4; anti-inflammatory cytokines IL-4, IL-10, TGF β).

In the absence of signs of pneumonia, patients in this group will undergo a single inhalation procedure, followed by a planar scintigraphy on a gamma camera at set intervals (see Item 7.3.2), and an assessment of the cytokine profile 3 hours after the procedure. The modes and geometry of measurements will strictly correspond to the modes and geometry of measurements on the phantom.

The study will enroll women and men aged 18 and over, hospitalized with a diagnosis of moderate new coronavirus infection (COVID-19) and receiving standard therapy.

Classification of COVID-19 by severity [11]:

Average, defined by the presence of at least one of the following signs:

- Fever above 38 ° C;
- NPV more than 22 / min;
- Shortness of breath during physical exertion;
- Pneumonia (susceptible to CT of the lungs);
- SpO2 <95%;
- CRP of blood serum more than 10 mg / l;

It is planned to include at least 10 patients in the protocol of a scientific prospective study.

All patients should undergo:

[figure not shown]
- laboratory test for confirmation of COVID-19 (PCR detection of SARS cov2 RNA);
- X-ray computed tomography of the thoracic organs, in which the presence of viral pneumonia is confirmed;
 - the levels of cytokines in blood plasma were determined (TNF α , IL-6, IL-12 TNF- α E, IL-4, IL-10, TGF β , interferon- γ -inducible protein (IP-10), monocyte chemoattractant protein 1 (MCP-1)
 - an assessment of the immune status was carried out,
 - biochemical indicators (levels of immunoglobulins and CEC) and indicators of the blood coagulation system (hemostasiogram) were evaluated;

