7.1 Methodology for obtaining and introducing UFCNPA, ^{99m}Tc

It is necessary to connect an argon gas cylinder to the TechnegasPlus generator and open the gas cylinder, connect the TechnegasPlus generator to the mains, turn on the TechnegasPlus generator and open the drawer. Remove the charcoal crucible from its packaging and place it on a watch glass. Before adding sodium pertechnetate, ^{99m}Tc ($\text{Na}^{99m}\text{TcO}_4$), it is necessary to moisten the crucible using absolute or 95% ethyl alcohol,

then the moistened crucible must be placed in the contacts of the drawer section. Next, the crucible must be filled with sodium pertechnetate, ^{99m}Tc ($\text{Na}^{99m}\text{TcO}_4$) with a volume of 0.1 to 0.3 ml with the required specific activity and close the drawer section. Start a slow heating cycle at the end of which, if necessary, you can refill the crucible with sodium pertechnetate, ^{99m}Tc ($\text{Na}^{99m}\text{TcO}_4$) to increase the specific activity, and repeat the slow heating cycle. Upon reaching the required specific activity, start the firing cycle, which consists in a short-term increase in temperature to 2700 ° C in an argon atmosphere, after which UFCNPA, ^{99m}Tc is ready for use within 10 minutes. After that, it is necessary to close the gas cylinder and disconnect it from the TechnegasPlus generator, turn off the TechnegasPlus generator and disconnect it from the mains.

For best results, ^{99m}Tc -labeled carbon ultrafine aerosol must be administered to the patient as soon as possible after being generated, and certainly within the 10 minutes allowed. The ^{99m}Tc -labeled carbon ultrafine aerosol is introduced to the patient through a series of deep and slow breaths with a 5 second delay of each breath through a special system of tubes and filters with a check valve. Before and during the inhalation of the ^{99m}Tc -labeled carbon ultrafine aerosol, all patients and volunteers will be tested for the degree of blood oxygen saturation (pulse oximetry).

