2) laboratory parameters assessment - during the in-patient period, in accordance with clinical need, but at least 4 times: before the start of RT, in 1, 3, 7 days after irradiation, and before the patient's discharge, cytokine levels - after 3 hours and after 10-12 hours from the procedure.

Table 2.

Methods of assessment	Terms
X-ray CT of thoracic organs	Before treatment, on 7 th and 14 th days after radionuclide therapy, or according to indications
Complete blood count (detailed)	- before treatment - on 1 st and 3 rd days after irradiation, then, according to indications, once every 2-3 days
ALT, AST, bilirubin, glucose, albumin, creatinine, LDH, lactate, electrolytes	- - before treatment - on the 1 st and 3 rd days after irradiation, then, according to indications, once every 2-3 days
CPK, troponin, C-reactive protein, IL-6, NT-proBNP, ferritin, procalcitonin	- before treatment - on the 1 st , 3 rd и 7 th days after treatment after irradiation, then, according to indications,
Coagulogram (APTT, prothrombin time, D-dimer)	- before treatment - on the 1 st , 3 rd и 7 th days after treatment after irradiation, then, according to indications,
Immunogram	- before treatment - on the 1 st , 3 rd и 7 th days after treatment after irradiation, then, according to indications,
Antibodies to SARS cov2 A, M, G	- before treatment - on the 7 th day after treatment after irradiation, then, according to indications,
Cytokine profile	before treatment, 3 hours after the procedure, 12 hours after the procedure, on the 3 rd and 7 th days after irradiation

10. Statistical Analysis Plan

Laboratory indicators were evaluated in accordance with the GLP criteria and with the laboratory standards for them. The assessment of biochemical parameters, the levels of circulating immune complexes and the antibody response to the SARS-cov2 pathogen was carried out on an automatic analyzer AU 480 (Becman Coulter). The hemostasis parameters were evaluated using an ALC Elit PRO automatic analyzer and a TAG 5000 thromboelastograph. The evaluation of immunological parameters was carried out in the direct immunofluorescence reaction with the detection of the results by 6-parameter flow cytometry on the FACS Canto II. Flow cytometry data were processed in the FCS3.0 and Kaluza software applications (Becman Coulter).

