Statistical data processing was carried out using the SPSS 2020 program for Windows. The statistical analysis included an estimate of the average values for the sample size, the average value, the minimum and maximum values, the standard deviation, the sum, and the standard error of the average.

To determine the reliability of the differences in the indicators, a T-test for independent variables was used, where for each variable being compared, the sample size, the average value, the standard deviation and the standard error of the average value were compared. For the difference between the means: the average value, standard error, and confidence interval is assumed to be 95%, the significance of the differences is considered reliable at $p < 0.05$ and highly reliable at $p < 0.0001$. The Levin's criterion of equality of variances and the t-criterion of equality of averages for both the combined and separate variances are used.

11. References

4. Burch WM. Evidence for the long-term biological distribution of Technegas particles. *Nucl Med Commun.* 1993;14(7):559-561. doi:10.1097/00006231-199307000-00007.
5. <https://jcsmr.anu.edu.au/research/projects/technegas/clinical-issues-of-technegas-use>.
6. Sampson CB: Adverse reactions and drug interactions with radiopharmaceuticals. *Drug Saf* 8:280-294, 1993.
8. Gaurav Dhawan, Rachna Kapoor, Rajiv Dhawan, Ravinder Singh, Bharat Monga, James Giordano, and Edward J. Low dose radiation therapy as a potential life saving treatment for COVID-19-induced acute respiratory distress syndrome (ARDS). *Calabreseh Radiother Oncol.* 2020 Jun; 147: 212–216.

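### Section 10's only comparison test is an unpaired t-test, although Table 2 schedules repeated measurements in the same patients

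*Combined protocol and SAP*

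**What the plan says.** Section 10 gives the comparison method in one sentence: "To determine the reliability of the differences in the indicators, a T-test for independent variables was used". It continues: "The Levin's criterion of equality of variances and the t-criterion of equality of averages for both the combined and separate variances are used". Levene's test with pooled- and separate-variance t-tests is the standard two-sample procedure, so the word independent is not a slip of translation. Intervals are at 95% and significance is at p < 0.05. No paired, change-from-baseline, repeated-measures or rank method is named, and the section does not say which means are to be compared.

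Sections 5 and 6 describe no control arm and no comparison between groups. On numbers, Section 6 says: "It is planned to include at least 10 patients in the protocol of a scientific prospective study". Before them, 5 volunteers without pneumonia take part in a dosimetry stage.

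The measurements are repeated within people. The cytokine row of Table 2 (Section 9) reads "before treatment, 3 hours after the procedure, 12 hours after the procedure, on the 3 rd and 7 th days after irradiation". CT, blood count, biochemistry, coagulation, immunogram and antibodies are likewise taken before treatment and again afterwards. In Section 6 the volunteers have cytokines assessed at the outset and then "an assessment of the cytokine profile 3 hours after the procedure".

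On safety, the objective in Section 5 begins "To determine the possibility, safety and effects of the use of inhaled low-dose radionuclide therapy". Section 7.1 has SpO2 read by pulse oximetry before and during inhalation in every patient and volunteer. Section 3 records "transient hypoxia caused by an average 8.5% decrease in oxygen saturation" in earlier use of the same aerosol. Neither SpO2 nor adverse events are listed in Table 2 or Section 10. Section 8.3 mentions toxicity only as an example of a reason for leaving the study.

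**The concern.** The one comparison that the schedule clearly supports is change within a person, from before inhalation to after it. Two readings from one patient usually resemble each other more than readings from two patients. A two-sample test treats the readings as if they came from different people, so its standard error keeps the between-person variation that pairing would remove.

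With about 10 patients, that loss matters. Moderate changes in cytokines or laboratory values could be reported as no reliable difference because of the test chosen, and the intervals would understate what the data show.

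A smaller matter sits beside this. SpO2 during inhalation is the within-person measurement closest to the acute effect described in Section 3. The plan gives no rule for summarising it or for counting adverse events.

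**Working it through.** The plan states no SD, correlation, effect size, power or sample-size calculation, so it has no figure to reproduce. The check compares the two tests on the same before/after data.

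**Inputs.** From the documents: at least 10 patients and 5 volunteers (Section 6); 95% intervals and p < 0.05 (Section 10), taken as two-sided. Assumed: normal readings, equal SD before and after, and within-person correlation ρ of 0, 0.3, 0.5 or 0.7.

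**Interval width.** The half-widths of the 95% interval for the mean difference are:

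- independent: t(0.975, 2n − 2) × SD × √(2/n)
- paired: t(0.975, n − 1) × SD × √(2(1 − ρ)/n)

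For n = 10 the independent half-width is 2.101 × √0.2 = 0.940 SD, whatever the correlation. The paired one at ρ = 0.5 is 2.262 × √0.1 = 0.715 SD, and 0.940/0.715 = 1.31. For n = 5 the independent half-width is 2.306 × √0.4 = 1.458 SD.

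| ρ | Paired, n = 10 (SD) | Ratio independent/paired | Paired, n = 5 (SD) | Ratio independent/paired |
|---|---|---|---|---|
| 0 | 1.012 | 0.93 | 1.756 | 0.83 |
| 0.3 | 0.846 | 1.11 | 1.469 | 0.99 |
| 0.5 | 0.715 | 1.31 | 1.242 | 1.17 |
| 0.7 | 0.554 | 1.70 | 0.962 | 1.52 |

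The ratio has two parts. Ignoring the pairing inflates the standard error by 1/√(1 − ρ): 1.20, 1.41 and 1.83 at ρ = 0.3, 0.5 and 0.7. Against that, the independent test has more degrees of freedom, a factor of 2.101/2.262 = 0.93 at n = 10. At ρ = 0 only the second part remains, so pairing costs a little there. The separate-variance version does not help: with equal numbers before and after, its standard error equals the pooled one.

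**Type I error.** The independent t-test was applied to simulated bivariate normal pairs with no true change, n = 10. Its rejection rate at the nominal 0.05 is 0.050, 0.023, 0.010 and 0.002 at ρ = 0, 0.3, 0.5 and 0.7.

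**Power, as an illustration.** For an assumed true change of 0.8 SD and n = 10:

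| ρ | Independent | Paired |
|---|---|---|
| 0 | 39% | 36% |
| 0.3 | 38% | 48% |
| 0.5 | 37% | 62% |
| 0.7 | 35% | 83% |

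**Adverse events.** The exact two-sided 95% upper limit for no events in n people is 1 − 0.025^(1/n). For 0/10 this is 1 − 0.025^0.1 = 30.8%.

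**The case against.** The strongest reply is that Section 10 never says which means are compared, so it does not expressly assign the independent test to before/after data. Two different groups do have cytokines measured at baseline and 3 hours, the volunteers and the patients, and an independent t-test has the right form for that contrast. This stands in part: the fault applies when the test is used within people. But the plan states no volunteer-versus-patient comparison. The groups also differ in disease and in activity loaded (833 against 4165 MBq), and even if that contrast were intended, the repeated measurements would be left with no comparison method.

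A second reply is that the error is conservative, breaks no stated power target, and leaves the raw paired data available for a later analysis. This is correct and limits the weight of the point. For the volunteers at correlation 0.3 there is no loss of width at all (ratio 0.99).

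Two stronger readings are tempting and are not supported:

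- A reader might infer that the wrong test would produce false claims of benefit. With positive within-person correlation the false-positive rate of the individual test falls below 5%.
- A reader might infer that the plan collects no safety data or can give no SpO2 result. Section 7.1 has SpO2 read in everyone, the descriptive statistics in Section 10 are not restricted to Table 2 items, and Table 2 schedules ALT, AST, creatinine, troponin, blood count, coagulation and CT. Section 10 assigns no test to SpO2, so it cannot be said that the plan would test SpO2 wrongly. Section 3 also reports the view that the earlier saturation fall did not appear to endanger patients.

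**Conclusion.** The point holds: the only comparison test named does not fit the repeated measurements that make up the schedule. At n = 10 the cost is an interval 11%, 31% or 70% wider than necessary at correlation 0.3, 0.5 or 0.7, with a matching loss of power for moderate changes. These sizes rest on assumed correlations, equal SDs and normality. There is no loss at correlation 0, and the conservative direction depends on the correlation being positive, which is usual for repeated readings but not documented here.

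The safety element is secondary. What is missing is a rule for reporting SpO2 change and a definition and count of adverse events, not safety data as such.

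**What to change.** 1. In Section 10, for any indicator measured more than once in the same person, report the mean within-person change from the pre-treatment value with a paired 95% confidence interval. For skewed cytokines, work on the log scale or use the Wilcoxon signed-rank test. State that results across the many indicators and time points are exploratory. Keep the independent t-test only for comparisons between different people, and name them if any are intended.
2. Add SpO2 to Table 2 with stated reading times. Report the paired change, pre-inhalation minus the mean of the readings during inhalation (or one fixed-time reading), separately for volunteers and patients.
3. Define an adverse event, its grading and a recording window, for example from the start of inhalation to day 14. Report the number of patients with any event, with an exact confidence interval, over everyone who began inhalation, including those later removed under Section 8.3.
4. State that, without controls, neither a within-person change nor an adverse event can be attributed to the inhalation rather than to COVID-19 and its standard treatment.

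The cost is small. Item 1 is a wording change that uses data already planned, item 2 adds one row to Table 2 for a measurement already made, item 3 needs a definition and one recording form, and item 4 is one sentence.

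### Section 10 tests every difference with an independent-samples t-test and states no contrast; for before/after values in the same patients, the main comparison the design offers, that test ignores the pairing

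*Combined protocol and SAP*

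**What the plan says.** Section 10 is the whole inferential plan. After a list of descriptive statistics it states that "a T-test for independent variables was used" to judge differences in the indicators. This is not a loose translation of some other test, because the section also calls for a test of equal variances and says that the "t-criterion of equality of averages for both the combined and separate variances are used". Those are the two standard forms of the independent-samples test. The "confidence interval is assumed to be 95" percent, and "the significance of the differences is considered reliable at" p<0.05, with a higher grade at p<0.0001.

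The section does not say which groups or times are compared. It names no main marker or time, and it does not call the tests exploratory. Nothing elsewhere fills these gaps: Section 5 gives a broad aim covering possibility, safety and effects.

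The data structure is in Sections 6 and 9. At least 10 patients are to be enrolled and treated. Section 9 sets "laboratory parameters assessment - during the in-patient period, in accordance with clinical need", and continues with a minimum of four occasions including baseline and days 1, 3 and 7. Table 2 has the cytokine profile "before treatment, 3 hours after the procedure, 12 hours after the procedure", and again on days 3 and 7. The only other people studied are 5 volunteers without pneumonia, who also have cytokines measured before and 3 hours after a single inhalation. No untreated patients are described.

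**The concern.** With one treated group measured at baseline and again afterwards, the natural question is whether each marker changed. Two values from the same patient are usually correlated, and a paired analysis uses that correlation to remove between-patient variation. An independent-samples test treats the two sets of values as coming from different people, so its standard error is wrong whenever the correlation is not zero. If the correlation is positive, the interval is too wide and real changes are missed. If it is negative, the test rejects too often. With about 10 patients there is little information to spare.

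A second, smaller matter is the labelling. Every marker at every time is open to the same p<0.05 rule, and a result called reliable may be read as evidence of effect. How far this matters depends on which test is used, so the two matters should be handled together.

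**Working it through.** The plan gives no power, precision or error-rate figure, so there is nothing to reproduce. The check asks what the named test does to before/after data.

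**Inputs**
- From the documents: n = 10 patients (the Section 6 minimum), threshold 0.05 and a 95% interval (Section 10). Two-sided testing is assumed, in line with the 95% interval.
- Assumed: normal data (or normal on the log scale), equal SDs at both times, all 10 patients measured at both times, and within-patient correlation r = 0.2 / 0.5 / 0.8. The cases r = 0 and r = -0.3 are shown because they go the other way.

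**Interval width.** With common SD s, the half-widths are:
- independent: t(18) × s × √(2/n)
- paired: t(9) × s × √(2(1−r)/n)

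The ratio is 2.101 / (2.262 × √(1−r)). At r = 0 / 0.2 / 0.5 / 0.8 this gives 0.93 / 1.04 / 1.31 / 2.08. The ratio is 1 when r = 1 − (2.101/2.262)² ≈ 0.14. Below that the paired interval is slightly wider, because it has 9 rather than 18 degrees of freedom.

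**False-positive rate, coverage and power.** Rates for the independent test come from simulation with at least 200,000 data sets per setting. Paired power is exact, from the noncentral t with noncentrality √10 / √(2(1−r)) for a 1 SD change. Coverage is 1 minus the false-positive rate.

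| r | Independent: false-positive rate | Independent: coverage of 95% CI | Power, 1 SD: independent | Power, 1 SD: paired |
|---|---|---|---|---|
| −0.3 | about 8% | about 92% | 56% | 42% |
| 0 | 5.0% | 95% | 56% | 51% |
| 0.2 | 3.1% | 97% | 57% | 61% |
| 0.5 | 1.0% | 99% | 59% | 80% |
| 0.8 | 0.05% | 99.95% | 62% | 99% |

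The paired false-positive rate is 5% in every row. At r = −0.3 the independent test's apparent power advantage comes with an inflated error rate. The separate-variance form behaves almost identically (3.0 / 0.9 / 0.05% at r = 0.2 / 0.5 / 0.8).

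**How many comparisons are open to the rule.** This counts fixed post-treatment times in Table 2 and the eight patient cytokines in Section 6. Blood count and immunogram are left out because their parameters are not listed.
- "ALT, AST, bilirubin, glucose, albumin, creatinine, LDH, lactate, electrolytes", with electrolytes as one item: 9 × 2 = 18
- "CPK, troponin, C-reactive protein, IL-6, NT-proBNP, ferritin, procalcitonin": 7 × 3 = 21
- coagulation: 3 × 3 = 9
- antibodies: 3 × 1 = 3
- cytokines: 8 × 4 = 32, less 2 IL-6 values already counted on days 3 and 7 = 30

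The total is 81. Leaving electrolytes out gives 79. Adding the day 7 biochemistry implied by the Section 9 text gives 90. So the figure is roughly 80, and these are opportunities for a test, not committed tests.

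Expected chance labels if no cell truly changed:
- valid paired 5% test: 81 × 0.05 ≈ 4
- independent test as written, r = 0.2 / 0.5 / 0.8: 81 × 0.0309 / 0.0096 / 0.0005 ≈ 2.5 / 0.8 / 0.04

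**The case against.** The strongest objection is that the plan never says it will compare before with after. It could mean volunteers against patients, or one patient subgroup against another, since Section 8.1 admits patients over 65 with or without early cytokine-storm signs. An independent-samples test would be valid for either. That stands, and the pairing criticism is conditional for this reason. But no such contrast is stated either. Volunteers and patients differ in disease and in loaded activity (833 against 4165 MBq), so that comparison could not estimate a treatment effect.

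The second objection is that the correlation is assumed. That also stands. Positive correlation is usual for repeated laboratory values in one person, but the documents give no figure, and near zero the paired test is slightly weaker.

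The third is that this is a small study with a feasibility and safety aim, so labels are a matter of reporting style. In part that is fair: an exploratory label or a named main marker would not carry the point alone. The test itself is different, because it produces an interval of the wrong width for the main data in hand.

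A reader might infer that the plan as written will produce about 4 chance findings. The documents do not support that. On before/after data with positive correlation the named test is conservative, and the figure of about 4 arises only once the test is made paired and the old rule is kept. A reader might also infer from the exclusion of patients with a forecast stay under 48 hours that later measurements will be largely missing. That criterion is a floor, not an expected stay. Section 9 schedules laboratory work to day 7 and CT to day 14, and gives no attrition figure.

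**Conclusion.** The point holds in conditional form. Section 10 leaves the contrast unstated and names only an independent-samples test, while the main comparison the design offers is within patients. If that comparison is intended, the analysis is mis-specified: at assumed correlations of 0.5 to 0.8 and n=10, the interval is about 1.3 to 2.1 times wider than needed, and power for a 1 SD change falls from 80–99% to 59–62%. At 0.2 the loss is small. At zero there is a slight gain from the test as written (56% against 51%). At negative correlation it rejects too often. These figures rest on normality, equal SDs and complete data in 10 patients.

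The labelling issue is secondary. It becomes material mainly when the test is corrected, which is why both belong in one edit. The plan should be changed, but the defect is one of analysis wording and does not affect what data are collected.

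**What to change.** Make one edit to Section 10:

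1. State which groups and times are compared.
2. For every comparison within the same patients, replace the independent test with paired change from baseline, on the log scale for skewed markers, and report it with its 95% CI.
3. Keep the independent-samples test only for comparisons between different people, such as volunteers against patients or patient subgroups.
4. Label the laboratory comparisons exploratory and remove the two reliability grades.

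The cost is SAP wording; no new data or patients are needed. Fewer results can be called significant, and a little power is lost if within-patient correlation is near zero. The edit leaves one limit untouched: with no concurrent untreated patients described, a before/after change cannot be attributed to the inhalation rather than to standard therapy or the course of the illness.
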